8.2.3.2.3 Specimens Taken Outside the Context of the Study

Tissue biopsies collected outside the context of the study are strongly discouraged. "Outside the context of the study" is defined as processing of samples at a local laboratory rather than

V503-064-03 FINAL PROTOCOL 24-SEP-2024

Confidential

through the Sponsor-designated Central Laboratory. If a participant undergoes a biopsy outside the context of the study, all efforts will be made to obtain the operative report, local pathology report, diagnostic slides (for tissue biopsies), tissue block for slide preparation, PCR analysis and pathology panel review.

8.2.3.3 HPV DNA PCR Assay

The HPV PCR Assay developed and published by MSD [Else, E. A., et al 2011] [Roberts, C.C., et al 2011] is a multiplexed real-time type-specific PCR assay. The PCR assay has been used in previous efficacy studies that supported the licensure of GARDASIL® and GARDASIL®9/SILGARD®9. The PCR assay is validated for the detection of HPV DNA of 14 HPV types, including the 12 HPV types that have been recognized as oncogenic by the International Agency for Research on Cancer (including HPV 16, 18, 31, 33, 35, 39, 45, 51, 52, 56, 58, and 59) [Bouvard, V., et al 2009] and the low-risk types HPV 6 and 11.

HPV vaccine types 6, 11, 16, 18, 31, 33, 45, 52, and 58 will be analyzed using this type-specific multiplex (L1, E6, and E7 gene detection) PCR assay. HPV types 35, 39, 51, 56, and 59 will be detected using a duplex (E6 and E7 gene detection) PCR assay using the preparation method described below.

Specimens are received and prepared for multiplex PCR using a DNA purification method (Qiagen Technology Kit). Multiplex PCR (based on real-time fluorescent PCR) allows the simultaneous detection of 3 gene products (L1, E6, and E7) for a given HPV type in 1 reaction. The HPV type-specific primer pairs based on the published HPV L1, E6, and E7 sequences, are used to specifically amplify a portion of each gene simultaneously. The specific amplicons are detected in real-time by fluorescently labeled oligonucleotide probes. The gene-specific oligonucleotide probes are each labeled with a different fluorescent label, and the fluorescent emission is captured during PCR cycling. After analysis of the raw fluorescent data by the real-time PCR instrument software, a threshold cycle (Ct), which represents the PCR cycle at which an increase in reporter fluorescence above a baseline signal can first be detected, is determined. Each gene-specific assay (ie, gene-specific dye layer) is considered positive if the Ct is <45 cycles. A gene-specific assay is considered negative if the Ct = "No Ct". A sample is called positive when 2 or 3 genes are positive or when the same single gene scores positive on consecutive tests. The assay has been validated for swab and tissue specimens.

8.3 Immunogenicity Assessments (Base Study)

8.3.1 Blood Sample Collection for Serum Anti-HPV Antibody Testing

In the base study, blood samples will be collected for analysis of antibodies specific for HPV 6, 11, 16, 18, 31, 33, 45, 52, and 58 titers in serum. On Day 1, blood samples will be collected prior to the first study vaccination to identify participants who have been exposed to study vaccine HPV types prior to enrollment. Serology results at Day 1 are not part of the inclusion/exclusion criteria; thus, no participant will be excluded from the study based on these results. After Day 1, serum specimens will be collected at Month 7, and Month 36 (or Final Visit) to evaluate persistence of immune responses.

V503-064-03 FINAL PROTOCOL 24-SEP-2024

Blood sample collection, storage, and shipment instructions for serum samples will be provided in the Laboratory Manual. Blood samples will be collected for anti-HPV antibody testing per the schedule indicated in the SoA (Section 1.3).

After completion of immunogenicity testing to evaluate the study objectives and hypotheses, all leftover serum samples will be stored for up to 15 years. The samples may be used to conduct any additional study-related testing, biomarker testing, or to support HPV assay development/validation activities as required by regulatory agencies or the Sponsor.

8.3.2 Competitive Luminex Immunoassay

The 9-valent HPV cLIA will be used as a primary method to evaluate antibodies specific for HPV 6, 11, 16, 18, 31, 33, 45, 52, and 58 in serum. The purpose of the assay is to detect these HPV antibodies before and after vaccination with the 9vHPV vaccine in the base study. The testing will be performed by Q Squared Solutions (California, USA).

For the 9-valent HPV cLIA, HPV type-specific, yeast-derived VLPs are coupled to 9 distinct Luminex magnetic microspheres. Each VLP-coupled microsphere has its own distinct fluorescent dye that can be recognized by excitation with an infrared laser, allowing for the measurement of antibodies against multiple HPV types from a single test of an individual's serum. HPV type-specific monoclonal antibodies labeled with R-Phycoerythrin (PE) compete with an individual's serum antibodies for binding to the neutralizing epitopes of the VLPs. The fluorescent signal from the PE-labeled, type-specific monoclonal antibodies is inversely proportional to the anti-HPV antibody concentration of a sample. Antibody concentrations are derived from a standard curve, which is generated using a reference standard made from a pool of serum from individuals immunized against the nine HPV types. A standard curve for each HPV type is calculated using a weighted 4 parameter logistic curve fit. Results are expressed as milli-Merck Units/ml (mMU/mL).

The assay was validated at Q Squared Solutions. Validation evaluated precision, linearity, LLOQ, ULOQ, and relative accuracy/dilutability for the quantitation of antibodies specific to HPV types 6, 11, 16, 18, 31, 33, 45, 52, and 58. Serostatus cutoffs for each HPV type will be predefined. A participant will be considered seropositive to a given HPV type at Day 1 of the base study if the participant's anti-HPV titer, as assessed by cLIA, is greater than or equal to the corresponding serostatus cutoff for that HPV type. A participant will be considered seronegative to a given HPV type at Day 1 of the base study if the participant's anti-HPV titer, as assessed by cLIA, is less than the corresponding serostatus cutoff for that HPV type.

8.4 Safety Assessments

Details regarding specific safety procedures/assessments to be performed in this study are provided.

Planned time points for all safety assessments are provided in the SoA.

V503-064-03 FINAL PROTOCOL 24-SEP-2024 Confidential 70

8.4.1 **Physical Examinations**

A physical examination is optional and will be conducted by an investigator on Day 1 of the base study to determine whether the participant meets eligibility criteria for enrollment.

Height and weight will be recorded on Day 1 of the base study before administration of the study vaccine.

Physical examination details will be recorded in the participant's study chart. Any medical condition identified during physical examination will be documented in the data collection system. Investigators should pay special attention to clinical signs related to previous serious illnesses.

8.4.2 **Oral Temperature Measurements**

In the base study, oral temperature will be assessed before study vaccine is administered on Day 1, Month 2, and Month 6 visits. If the participant has a fever (defined as an oral temperature of ≥ 37.5 °C) within the 24-hour period prior to receiving a study vaccination, the participant should not receive the study vaccine, and the vaccination visit should be rescheduled until after the fever has resolved.

Postvaccination, if an oral temperature indicates a fever (defined as an oral temperature of \geq 37.5°C), then an AE of "fever" must be documented in the eCRF.

In the extension study, oral temperature will be assessed before 9vHPV vaccine is administered at the visits specified in Section 1.3.2 and Section 1.3.3 of the SoA.

8.4.3 **Clinical Safety Laboratory Assessments**

There will be no protocol-specific clinical safety laboratory assessments for this study. If laboratory values from non-protocol-specified laboratory assessments performed at the institution's local laboratory require a change in study participant management or are considered clinically significant by the investigator (eg, SAE or AE or discontinuation of the study vaccine), then the results must be recorded in the appropriate case report form (CRF) (eg, SLAB).

8.4.4 **Vaccination Report Card**

Base Study:

The investigator or delegate will train the participant in the use of the VRC at Visit 1 (Day 1). Temperatures, injection-site reactions, other complaints or illnesses, and concomitant medications or vaccinations will be recorded on the VRC by the participant. Participants should be informed to contact the investigator immediately in the event of a hospitalization or visit to another physician.

V503-064-03 FINAL PROTOCOL 24-SEP-2024 Confidential

Participants will use the VRC to document the following information:

- Oral temperatures measured Day 1 (day of vaccination) through Day 5 postvaccination.
 - Participants will record oral temperature in the evening after each study vaccination and daily, at the same time of day, for 4 days after each study vaccination for the purpose of identifying febrile events.
 - Note: If an oral temperature indicates a fever (defined as an oral temperature of ≥ 37.5 °C), the AE of "fever" must be documented in the appropriate eCRF.
- Solicited injection-site AEs (redness/erythema, swelling, and tenderness/pain) Day 1 through Day 5 postvaccination.
- Any other injection-site or systemic AEs Day 1 through Day 15 postvaccination.
- Concomitant medications and non-study vaccinations Day 1 through Day 15 postvaccination.

In order to ensure that the VRC is being filled out without delay, telephone contacts to remind the participant will be conducted after 15 days postvaccination.

All participants will be expected to bring the VRC to the study site at the next scheduled visit. The investigator or delegate will review the data captured on the VRC with the participant at Visit 2 (Month 2), Visit 3 (Month 6), and Visit 4 (Month 7). For the AEs outlined above, the investigator will use the information provided by the participant both on the VRC, and verbally at the time of VRC review, to apply the appropriate assessment of causality as described in Appendix 3. At the time of VRC review at the next scheduled visit, participants will be questioned regarding any new medical conditions that occurred beyond Day 15 postvaccination. The investigator will determine if the medical condition is to be reported as an SAE using the reporting guidelines provided in Section 8.4.

Extension Study:

A VRC will not be utilized for participants enrolled in the extension study and NSAEs will not be collected. SAEs and death will be collected from the first dose of vaccination until 1 month after the last dose.

8.4.5 Postvaccination Observation Period (30 Minutes)

In both the base study and study extension, all participants will be observed for at least 30 minutes after each vaccination for any immediate reactions. If any immediate AEs (including allergic reactions) are observed during this period, the time at which the event occurred within this timeframe, as well as the event itself, any concomitant medications that were administered, and resolution of the event, must be recorded on the appropriate eCRF.

V503-064-03 FINAL PROTOCOL 24-SEP-2024

8.5 Adverse Events, Serious Adverse Events, and Other Reportable Safety Events

The definitions of an AE or SAE, as well as the method of recording, evaluating, and assessing causality of AE and SAE and the procedures for completing and transmitting AE, SAE, and other reportable safety event reports can be found in Appendix 3.

Adverse events, SAEs, and other reportable safety events will be reported by the participant (or, when appropriate, by a caregiver, surrogate, or the participant's legally authorized representative).

The investigator and any designees are responsible for detecting, documenting, and reporting events that meet the definition of an AE or SAE as well as other reportable safety events. Investigators need to document if an SAE was associated with a medication error, misuse, or abuse.

Investigators remain responsible for following up AEs, SAEs, and other reportable safety events for outcome according to Section 8.5.3. The investigator, who is a qualified physician, will assess events that meet the definition of an AE or SAE as well as other reportable safety events with respect to seriousness, intensity and causality.

8.5.1 Time Period and Frequency for Collecting AE, SAE, and Other Reportable Safety Event Information

All AEs, SAEs, and other reportable safety events that occur after the participant provides documented informed consent, but before randomization, must be reported by the investigator if they cause the participant to be excluded from the study, or are the result of a protocol-specified intervention, including, but not limited to washout or discontinuation of usual therapy, diet, placebo, or a procedure.

Base Study:

From the time of randomization through 14 days following the first vaccination(s) and from the time of any subsequent vaccination(s) through 14 days thereafter, all AEs must be reported by the investigator. All SAEs and other reportable safety events that occur from the time of randomization through 6 months following the last vaccination must be reported by the investigator, regardless of whether the events are considered to be vaccine-related by the investigator.

Extension Study:

SAEs and death will be collected from the first dose of vaccination until 1 month after the last dose.

V503-064-03 FINAL PROTOCOL 24-SEP-2024

Base Study and Extension Study:

Additionally, any SAE brought to the attention of an investigator at any time outside the period specified in the previous paragraph also must be reported immediately to the Sponsor if the event is either:

• A death that occurs before the participant completing the study, but outside the period specified in the previous paragraph.

OR

• An SAE that is considered by an investigator, who is a qualified physician, to be vaccine related.

Investigators are not obligated to actively seek AEs or SAEs or other reportable safety events in former study participants. However, if the investigator learns of any SAE, including a death, at any time after a participant has been discharged from the study, and the investigator considers the event to be reasonably related to the study intervention or study participation, the investigator must promptly notify the Sponsor.

All initial and follow-up AEs, SAEs, and other reportable safety events will be recorded and reported to the Sponsor or designee within the time frames as indicated in Table 3.

Table 3 Reporting Periods and Time Frames for Adverse Events and Other Reportable Safety Events

Type of Event NSAE	Reporting Time Period: Consent to Randomization/ Allocation Report if: - due to protocol- specified intervention - causes exclusion - participant is receiving placebo run-in or other run-	Reporting Time Period: Randomization/ Allocation through Protocol- specified Follow- up Period Report all	Reporting Time Period: After the Protocol- specified Follow- up Period Not required	Time Frame to Report Event and Follow-up Information to Sponsor: Per data entry guidelines
SAE	in treatment Report if: - due to protocol- specified intervention - causes exclusion - participant is receiving placebo run-in or other run- in treatment	Report all	Report if: - drug/vaccine related any death until participant completion of study (Follow ongoing to outcome)	Within 24 hours of learning of event
Cancer	Report if: - due to intervention - causes exclusion	Report all	Not required	Within 5 calendar days of learning of event (unless serious)
Overdose NSAE=nonserious a	Report if: - receiving placebo run-in or other run- in medication dverse event; SAE=serious a	Report all	Not required	Within 5 calendar days of learning of event

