Scrotal file and wetted swab for HPV PCR	X		_	X	X	X	X	X	X	X	X	X	X	Prior to vaccination on Day 1 Sample should not be collected after initial database lock and unblinding.
Perianal examination for external genital lesions	X			X	X	X	X	X	X	X	X	X	X	Prior to vaccination on Day 1 Examination will not be required after initial database lock and unblinding.

Visit Number	1	2	3	4	5	6	7	8	9	10	11	12	13	Notes
	Day 1		Month											
Scheduled Day/Month		2	6	7	12	18	24	30	36	42	48	54	60 (Final Visit)	
Visit Window ¹		± 3 Weeks	± 4 Weeks	3 to 7 Weeks Postdose 3		± 1 month							To calculate visit windows, assume 1 month=30 days and 1 week=7 days	
Perineal/perianal file and wetted swab for HPV PCR	X			X	X	X	X	X	X	X	X	X	X	Prior to vaccination on Day 1 Sample should not be collected after initial database lock and unblinding.
Intra-anal wetted swab for HPV PCR	X			X	X	X	X	X	X	X	X	X	X	Prior to vaccination on Day 1 Sample should not be collected after initial database lock and unblinding.
External genital lesion biopsy (if indicated)		X	X	X	X	X	X	X	X	X	X	X	X	Processed and analyzed at Central Laboratory Sample should not be collected after initial database lock and unblinding.
Sexually Transmitted Infection (STI) Testing (local laboratory testing, at the discretion of the investigator if clinically indicated)	X	X	X	X	X	X	X	X	X	X	X	X	X	Optional at any visit
Blood Sample Collection (Serum for anti-HPV)	X			X					X				(X) ²	Prior to vaccination on Day 1 Sample should be collected even after initial database lock and unblinding.
Blood Sample Collection (DNA) for Future Biomedical Research	X													Prior to vaccination from enrolled participants only (optional).
Vaccine Allocation/Randomization	X													
9vHPV Vaccine/Placebo Administration	X	X	X											
30-minute postvaccination observation period	X	X	X											
Provide Vaccination Report Card (VRC)	X	X	X											See Section 8.4.4 for data collected in VRC.

Visit Number	1	2	3	4	5	6	7	8	9	10	11	12	13	Notes
	Day 1					Mon	th							
Scheduled Day/Month		2	6	7	12	18	24	30	36	42	48	54	60 (Final Visit)	
Visit Window ¹		± 3 Weeks	± 4 Weeks	3 to 7 Weeks Postdose 3				=	⊧ 1 mo	onth				To calculate visit windows, assume 1 month=30 days and 1 week=7 days
Review and Collect VRC		X	X	X										Telephone contacts after 15 days from Day 1, Month 2 and Month 6, respectively to remind the participants.
Monitor Adverse Events	X	X	X	X	X	X	X	X	X	X	X	X	X	

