Participants will be followed for solicited injection-site AEs Days 1 through Days 5 following each vaccination, and any other injection-site AEs and systemic AEs Days 1 through Days 15 following each vaccination. Any SAEs regardless of causality will be recorded from the time of randomization through 6 months postdose 3. Vaccine-related SAEs and deaths will be collected throughout the study. New medical conditions (defined as incident medical conditions occurring outside of Days 1 to Days 15 period following each vaccination and not considered SAEs) will be recorded for all participants at each study visit throughout the study.

The primary analysis is case driven. The database will be locked, and the primary analysis will be conducted after at least 17 primary efficacy endpoint cases and at least 17 secondary efficacy endpoint cases have been observed in the base study. There is no interim analysis planned in this study. These efficacy results as well as immunogenicity and safety results based on data in the initial database lock for the primary analysis will be reported as the primary CSR. All participants will be unblinded after the primary efficacy analysis database lock. Once a participant is unblinded, no further efficacy samples will be collected from the participant.

Once at least 17 primary endpoint cases and at least 17 secondary efficacy endpoint cases are accrued, each participant will proceed to the Final Visit promptly without completing any other scheduled visits in order to complete the base study (as shown in Section 1.3, and Section 8.12.1.4). Additional database locks will be executed, including a second database lock after the completion of the final efficacy sample assessment for the purpose of the final efficacy analysis and a final database lock of the base study after the last participant's Final Visit in the base study for the final immunogenicity and safety analysis, respectively. Cumulative data collected from the initiation of the study will be summarized separately and a report will be written after each database lock. The base study will end after the last participant completes their Final Visit in the base study.

Extension Study

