10.3.2 Definition of AE

AE definition

- An AE is any untoward medical occurrence in a clinical study participant, temporally associated with the use of study intervention, whether or not considered related to the study intervention.
- Note: An AE can therefore be any unfavorable and unintended sign (including an abnormal laboratory finding), symptom, or disease (new or exacerbated) temporally associated with the use of a study intervention.
- Note: For purposes of AE definition, study intervention includes any pharmaceutical product, biological product, vaccine, diagnostic agent, medical device, combination product, or protocol-specified procedure whether investigational or marketed (including placebo, active comparator product, or run-in intervention), manufactured by, licensed by, provided by, or distributed by the Sponsor for human use in this study.

Events meeting the AE definition

- Any abnormal laboratory test results (hematology, clinical chemistry, or urinalysis) or other safety assessments (eg, ECG, radiological scans, vital signs measurements), including those that worsen from baseline, considered clinically significant in the medical and scientific judgment of the investigator.
- Exacerbation of a chronic or intermittent preexisting condition including either an increase in frequency and/or intensity of the condition.

PROTOCOL/AMENDMENT NO.: 064-03

New conditions detected or diagnosed after study intervention administration even though it may have been present before the start of the study.

- Signs, symptoms, or the clinical sequelae of a suspected drug-drug interaction.
- Signs, symptoms, or the clinical sequelae of a suspected overdose of either study intervention or a concomitant medication.
- For all reports of overdose (whether accidental or intentional) with an associated AE, the AE term should reflect the clinical symptoms or abnormal test result. An overdose without any associated clinical symptoms or abnormal laboratory results is reported using the terminology "accidental or intentional overdose without adverse effect."
- Any new cancer or progression of existing cancer.

Events NOT meeting the AE definition

- Medical or surgical procedure (eg, endoscopy, appendectomy): the condition that leads to the procedure is the AE.
- Situations in which an untoward medical occurrence did not occur (social and/or convenience admission to a hospital).

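### In the late base study, a non-fatal SAE caused by a protocol-specified procedure has no explicit reporting trigger, unlike before randomization and after discharge

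*Combined protocol and SAP*

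**What the plan says.** SAE reporting depends on the period.

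- **Consent to randomization** (Section 8.5.1, Table 3): events are reportable if they exclude the participant or "are the result of a protocol-specified intervention". Section 8.5.1 names a procedure among the examples.
- **Randomization to 6 months after the last dose**: every SAE. Section 8.5.1 has "All SAEs and other reportable safety events that occur from the time of randomization through 6 months following the last vaccination must be reported", and Section 4.1 has "Any SAEs regardless of causality will be recorded from the time of randomization through 6 months postdose 3".
- **After that window, still enrolled** (Section 8.5.1): two triggers. The first is a fatal event in someone who has not yet finished the study. The second is worded as follows: "An SAE that is considered by an investigator, who is a qualified physician, to be vaccine related". The SAE row of Table 3 and Section 4.1 give the same two.
- **After discharge** (Section 8.5.1): an SAE that comes to the investigator's notice is reportable if "the investigator considers the event to be reasonably related to the study intervention or study participation".

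For the definition of an adverse event, Section 10.3.2 lists several kinds of product "or protocol-specified procedure whether investigational or marketed" as study intervention. A complication of a study biopsy or swab is thus an adverse event, and can be an SAE.

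Swabs are taken from four sites at Day 1, Months 7 and 12, and every 6 months to about Month 60. New lesions that may be HPV-related, or are of unknown cause, are biopsied (Sections 1.3.1, 4.1 and 8.2.3).

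**The concern.** Study procedures continue long after vaccination ends, and they are not trivial. Penile, scrotal and perineal/perianal skin is filed firmly enough to blanch it, a swab is passed into the anal canal, and lesions are removed with scissors or scalpel under local anaesthetic (Sections 8.2.3.1 and 8.2.3.2). Suppose a participant is admitted with bleeding or infection after a protocol biopsy at Month 24. That is an SAE under Appendix 3, but it is neither a death nor, on the plain words, vaccine related. The late in-study rule does not require the site to report it. A site that learned of the same event after discharging the participant would have to report it, as related to study participation.

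At stake is whether the sponsor, and through it the ethics committees and the other sites, would see a pattern of serious procedural harm. The synopsis states that there is no data monitoring committee, so reporting to the sponsor is the main way to detect one.

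**Working it through.** The plan states no figure to reproduce. The check has three parts.

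**1. Triggers side by side, for a non-fatal SAE**

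| Period | Vaccine related | Procedure related only |
|---|---|---|
| Consent to randomization | not applicable | reportable |
| Randomization to 6 months after last dose | reportable | reportable |
| Later base study, still enrolled | reportable | no trigger stated |
| After discharge | reportable | reportable, as study participation |

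Only the third row lacks a trigger for procedure-related events.

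**2. Other routes that might catch the event**

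- New medical conditions are recorded throughout the base study, but Sections 4.1 and 8.1.4 define them to exclude SAEs.
- The duty to detect and report in Section 8.5 and the 24-hour rule in Section 8.5.4 set no collection period of their own.
- Table 3 asks for all SAEs through the protocol-specified follow-up period. That period cannot be the whole study, because the next column provides separately for deaths up to study completion. The text of Section 8.5.1 ends it at 6 months.

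None of these closes the gap.

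**3. How much sampling falls after the window**

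Inputs: dose 3 at Month 6 ± 4 weeks; 30-day months, as Section 1.3.1 instructs; 6 months taken as 180 days; 11 sampling visits (Day 1 and Months 7, 12, 18, 24, 30, 36, 42, 48, 54, 60); 4 specimens per visit, so 11 × 4 = 44.

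Window end = day of dose 3 + 180.

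- Earliest dose 3: 152 + 180 = day 332, Month 11.1. Months 12 to 60 fall after it: 9 visits.
- On schedule: 180 + 180 = day 360, Month 12.0. Months 18 to 60 fall after it: 8 visits, 8 × 4 = 32 specimens.
- Latest dose 3: 208 + 180 = day 388, Month 12.9. 8 visits.

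As a share of a full 60-month (1800-day) base study, the time outside the window is 1 − 332/1800 = 82%, 1 − 360/1800 = 80% and 1 − 388/1800 = 78%.

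These are maxima. The study is case-driven, and sampling stops at unblinding (Sections 4.1 and 8.2.3). Section 9.9.1 projects the required cases within 56 months of the first consent, after 14 months of enrollment. If sampling stops at that point:

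- the first participant is at Month 56, with a last visit at Month 54: Months 18 to 54, 7 late visits, 28 specimens;
- the last participant is at 56 − 14 = Month 42: Months 18 to 42, 5 late visits, 20 specimens.

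Biopsies are additional and cannot be counted in advance.

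One group is more exposed. Section 8.5.1 counts from the last vaccination received, and Section 8.12.3 keeps participants who stop vaccination in the swab and biopsy schedule. For someone who stops after dose 1, the window ends at about Month 6, before all 10 post-baseline sampling visits.

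**The case against.** The best defence is that Appendix 3 already covers the case. Section 8.5 refers causality to that appendix, where the question is whether the study intervention caused the event, and study intervention includes a protocol-specified procedure for the purpose of the adverse event definition. An investigator who reasons that way could mark a biopsy complication as related and report it. This has some force: it cannot be said that such an event would never be reported, and the rule sets a minimum without forbidding further reports. But the late trigger says vaccine related, Table 3 says drug or vaccine related, and the causality guidance also speaks of the test product. The wider meaning is not carried into the rule that governs the period.

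It is also fair that the narrow late rule is stated consistently in three places, which suggests a deliberate choice. The documents give no reason for leaving procedures out of that choice.

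A reader might infer more than the text supports:

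- *That a biopsy complication is reportable before randomization.* The rule would cover it, but no biopsy is scheduled at Day 1 and a suspicious lesion then leads to exclusion. In practice the comparison concerns Day 1 swabs and the blood draw.
- *That the gap spans the whole study.* In the extension all SAEs are collected from the first extension dose to 1 month after the last, and efficacy sampling has stopped by then.
- *That sites would be unaware.* They perform the procedures, and adverse events are monitored at every base-study visit.
- *That unequal biopsy numbers would bias the safety comparison.* The planned SAE comparisons are Days 1 to 15 and vaccine-related SAEs at any time (Sections 9.4.3 and 9.6.3). A late SAE related only to a procedure enters neither.

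**Conclusion.** The point holds for the base study, from 6 months after the last vaccination until study completion. In that period a non-fatal SAE caused by a protocol-specified procedure has no explicit reporting trigger, and this does not fit the rules on either side of it or the definition in Appendix 3. It is a gap in safety reporting to the sponsor; no efficacy result and no planned safety comparison is affected.

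The visit counts measure exposure to procedures and not harm. They assume attendance as scheduled and, for the 5 to 7 late visits, that unblinding coincides with the projected 56 months; a lag between case accrual and unblinding could add a visit. With no serious complication rate in the documents, the number of missed reports cannot be estimated. The case for the change rests on participant safety and low cost.

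**What to change.** Make the same addition in three places:

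- **Section 8.5.1, second bullet**: an SAE considered by an investigator to be 'related to the study vaccine or to a protocol-specified procedure'.
- **Table 3, SAE row, column for the time after the follow-up period**: 'vaccine or study-procedure related' in place of the present drug/vaccine wording.
- **Section 4.1**: extend the sentence on what is collected throughout the study to SAEs that are vaccine related or study-procedure related, along with deaths.

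Changing only Section 8.5.1 and Table 3 would leave Section 4.1 in contradiction. The post-discharge rule, which speaks of study participation, would remain slightly wider, but the missing trigger would be supplied.

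The cost is a few words in each place and probably a few extra SAE reports. If efficacy sampling has already stopped when the change is considered, a retrospective query to sites for procedure-related SAEs after the 6-month window would recover the same information.
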